## **Part 2. Randomised controlled trial**

For the randomised controlled part of the trial, participants will be recruited with **early DD** to assess the efficacy of injections of adalimumab in controlling disease progression including nodule hardness.

A maximum of 200 participants will be randomised to participate in the study if they meet the inclusion/exclusion criteria and provide written consent. We will select participants with early disease nodules who also give a clear history of activation and progression of the disease in the previous 3-6 months. Only participants with flexion deformities of  $\leq 30^\circ$  at the metacarpophalangeal and/or at the proximal interphalangeal joint of their fingers will be recruited, with a maximum total flexion deformity of  $60^\circ$ . All participants will be screened for TB, Hepatitis B and C and HIV. If results are positive for any test, the participant will not be eligible to enter the trial and will be informed and counseled about the result of their test. The participants will be randomised (1:1) to receive injections of either adalimumab or saline (placebo) into the active nodule. The dose will be an injection into the nodule of 40 mg adalimumab, or the equivalent volume of saline. The adalimumab formulation of 40 mg in 0.4 ml formulation will be used. The adalimumab or placebo will be administered at 3 monthly intervals for the first year i.e. each participant will be injected on 4 occasions over a 9 month period (baseline, 3, 6 and 9 months) and followed-up for a further 9 months. If, on a returning visit, the nodule has reduced in size to such an extent that the clinician is not satisfied they can accurately deliver a repeat injection, then the clinician may decide to not inject on that visit. In this event, the participant will be invited to all further visits as originally planned, and future planned injections may be given if the nodule recurs.

Study participants will be seen at 6 time points after screening: week 0, 3 months, 6 months, 9 months, 12 months and 18 months according to the flow chart (Appendix B: Trial Flow Chart Part 2). The schedule, duration of each visit and visit window is detailed in the Schedule of procedures (Appendix C: Schedule of procedures Part 2). Study participants will be contacted by telephone by a member of the research team at 1 week post baseline to monitor for Adverse Events.

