### 3.2 Randomisation and Blinding

Randomisation will be undertaken at or prior to the baseline visit prior to receiving the trial injection. Participants will be randomised 1:1 to placebo or adalimumab with stratification by age and centre. Participants will be randomised through a secure online service provided by the Oxford Clinical Trials Research Unit (OCTRUE) called RRAMP. RRAMP is used to randomise participants and this will generate a Trial ID and prompt an email to Pharmacy which informs them of which IMP (drug or placebo) to dispense.

Full details of the randomisation are available in **RIDD\_RBP\_v9.0\_18May2018**, stored in the confidential statistical section of the TMF.

The methods for blinding will be influenced by the packaging of the adalimumab being used. For part 2, pre-filled syringe is the only option for using the 40mg in 0.4ml formulation. Due to the distinctive appearance of the syringe, it is not possible to blind the healthcare professional administering the injection to treatment allocation. To protect the quality of the data, any person injecting with a pre-filled syringe will NOT be involved in administering any further trial procedures. Any healthcare professionals involved with administering any trial procedure, including outcome assessments, after the injection of IMP will be blinded to treatment.

The IMP (which will be stored in pharmacy) will be dispensed with accountability to a member of the research team who will take the IMP to a clinic room separate from the participant. Care will be taken to ensure any healthcare professionals blinded to treatment allocation are not present for the injection, and the syringe will be hidden from the participant's view.

In summary, participants and healthcare professionals involved in participant follow-up and outcome assessment will always be blinded to treatment allocation. Laboratory staff will be blinded to treatment allocation.

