### 3.3 Sample Size

The sample size is based on unpublished data acquired in a pilot study 'Ultrasonographic (grey scale) characteristics of DD and their relationship to the clinical features and functional severity of the disease: a pilot study' (REC Ref. 11/SC/0447). Within the study there were 25 participants with mean nodule hardness of  $53 \pm 8$  for participants suffering DD and  $32 \pm 3$  for corresponding controls matched by age and sex.

Using the study, a minimum of 138 participants (69 per arm) would be required to detect a moderate effect size of 0.62, based on a 5 point change in nodule hardness at 12 months and assuming a standard deviation of 8 (5% significance (2-sided) and 90% power, allowing for a 20% loss to follow up).

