### 3.6 Blinded analysis

A blinded analysis of data (data analysed with no treatment information added) will be undertaken prior to the final data lock in order to clarify whether continuous variables are normally distributed and to identify participants who will be excluded from the per-protocol analysis.

Primary outcome measurements were conducted using two validated portable durometers. Following identification of potential issues with the initial study device with nodule hardness recording in patients with marked distortion of the skin close to their DD nodule, a second device which would not be affected by such distortions, was sourced and utilised. Patients in two study centres (Oxford and Edinburgh) had all subsequent measurements taken using both devices and patients in one study centre (Groningen) had all of their study measurements recorded using the newer device only. During the blinded analysis the results from the two durometers will be compared using a Bland-Altman plot. A cross-walk methodology will be used to map the results from the old tonometer to the results of the new tonometer, to allow maximum data utilisation. If this cross-walk is not effective in mapping the tonometer results, alternative measures may include favouring the results from the new device and using the results from the original device only where data for the new device are not available.

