### 3.7 Statistical Analysis Outline

In the RCT (**Part 2**), all analyses will be performed on participants randomised to **Part 2** only, on an intention-to-treat basis with sensitivity analyses run on the per protocol population.

The primary outcome measure is change in nodule hardness from baseline to 12 months. There will only be one dose level used in **Part 2**, which will be 40mg of adalimumab. It is expected that all nodules will be large enough to accommodate the injection, but if not the volume of residual IMP will be recorded. The difference in the mean change of nodule hardness between the two groups will be reported with 95% confidence intervals. The comparison of change in nodule hardness between interventions will be analysed primarily using Analysis of Covariance (ANCOVA) adjusting for baseline, if it is normally distributed. As a secondary confirmatory analysis, ANCOVA adjusting for baseline nodule hardness as well as the stratification factors comprising centre (Oxford, Edinburgh or Groningen) and age (as a continuous variable) will be conducted.

If the data are not normally distributed, the data will be log-transformed in order to gain normality and geometric means with 95% confidence intervals will be reported. If data are not normally distributed after log-transformation, the non-parametric Mann Whitney test will be used with no adjustment for baseline, and the median change with 95% confidence intervals will be reported.

In order to analyse change in nodule hardness over the full time period, linear mixed effects regression will be used to compare nodule hardness between interventions utilising all time-points up to 18 months and adjusting for stratification and other important prognostic factors.

The secondary outcome measures for **Part 2** include those for **Part 1** and also grip strength, range of motion and participant reported outcomes.

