## 6.2 Analysis methods: Primary outcome

The primary outcome analysis will be performed on the ITT population, comparing intervention (adalimumab) against placebo (saline, 0.9% NaCl) for all randomised participants with available nodule hardness data.

The adjusted difference in the mean change of nodule hardness between the two groups will be reported with 95% confidence intervals. The primary time point is 12 months. The primary analysis will be the comparison of change in nodule hardness between the adalimumab and saline groups using Analysis of Covariance (ANCOVA) adjusting for baseline nodule hardness, if it is normally distributed. If the data are not normally distributed, the data will be log-transformed in order to gain normality and geometric means with 95% confidence intervals reported. If data are not normally distributed after log-transformation, the non-parametric Mann-Whitney test will be used with no adjustment for baseline, and the median change with 95% confidence intervals will be reported.

As a supporting analysis, ANCOVA adjusting for baseline nodule hardness as well as the stratification factors comprising centre (Oxford, Edinburgh or Groningen) and age (as a continuous variable) will be conducted.

As a further supporting analysis, in order to analyse change in nodule hardness over the full time period, linear mixed effects regression will be used to compare nodule hardness between interventions utilising all available time-points up to 18 months and adjusting for stratification factors. Multilevel models permit all available data to be included in the analysis, thus eliminating complete case bias.

**Appendix 5: Outcome measure summaries, Table 8:** Mean (with SD) nodule hardness recorded at each study time-point.

**Appendix 5: Outcome measure summaries, Table 9:** Mean (with SD) nodule hardness at 12 months by number of injections received.

**Appendix 5: Outcome measures analysis, Table 17:** Nodule hardness ANCOVA and linear mixed-effects regression results for all follow-up time-points.

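### Randomisation is stratified by centre and age group, but the primary ANCOVA leaves both out and the adjusted model defines age in two ways (optional improvement)

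*SAP*

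**What the plan says.** SAP 3.2 sets out the allocation: "Participants will be randomised 1:1 to placebo or adalimumab with stratification by age and centre". Protocol 11.2 gives the age strata as 18-49 and 50 or over, and SAP Appendix 5, Table 5 marks age group and centre as the stratification variables.

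For the primary outcome, SAP 6.2 compares change in hardness between arms "using Analysis of Covariance (ANCOVA) adjusting for baseline nodule hardness, if it is normally distributed". Protocol 11.2 and SAP 3.7 name the same primary model. The model with the strata comes second in SAP 6.2: "As a supporting analysis, ANCOVA adjusting for baseline nodule hardness as well as the stratification factors comprising centre (Oxford, Edinburgh or Groningen) and age". Both are reported in Table 19 of SAP Appendix 5 (cited as Table 17 in SAP 6.2), the adjusted row beneath the baseline-only row.

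The form of age differs by place:

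| Place | Form of age |
|---|---|
| Protocol 11.2, primary and secondary outcomes | Two groups |
| SAP 3.7 (primary and secondary), 6.2 and 6.3 | Continuous |
| SAP Appendix 5, footnotes to Table 19 and the secondary-outcome results tables | Age group |

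SAP 3.7, for example, has "the stratification factors comprising centre (Oxford, Edinburgh or Groningen) and age (as a continuous variable) will be conducted".

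**The concern.** Stratified randomisation balances the arms on centre and age group, which makes the treatment estimate less variable when those factors are prognostic. A model that omits them does not credit that balance. It leaves their variance in the residual, so the standard error is overstated, the interval is too wide and the test is conservative. As planned, any such precision goes to a supporting row and not to the headline interval and p-value. Neither document gives a reason.

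The form of age is a separate matter and needs no assumption. A statistician following the SAP text and one following its table footnotes would fit different models for the same table row. SAP 7 plans an independent repeat of the primary and key secondary analyses, so the two could disagree while both followed the plan. An unsettled form also leaves a choice that could be made after results are seen.

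**Working it through.** **1. The plan's own sample size.** SAP 3.3 uses an effect size of 0.62 (5 points), "assuming a standard deviation of 8 (5% significance (2-sided) and 90% power, allowing for a 20% loss to follow up".

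- n per arm = 2 × (1.960 + 1.282)² / 0.62² = 54.7, so 55.
- Allowing for 20% loss: 55 / 0.80 = 68.75, so 69 per arm and 138 in total.

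This matches the stated figure. It uses the full SD of 8, so it claims no gain from any covariate.

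**2. What the strata could add.** Let R² be the share of post-baseline variance explained by centre and age group. The documents give no value, so 0 to 10% is assumed. With R² known, the residual SD becomes 8 × √(1 − R²), and the baseline-only interval is wider by about 1/√(1 − R²), less a small cost for estimating 3 extra coefficients. At R² = 10%, 1/√0.90 = 1.054.

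A simulation puts figures on this.

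- From the documents: N, 20% loss and SD 8.
- Assumed, because the randomisation document is not available: three equal centres, 20% of participants under 50, permuted blocks of 4, and R² split two thirds centre and one third age.
- Runs: 20,000 under the null (Monte Carlo SE about 0.15 points) and 8,000 at a 5-point difference (about 0.3 points).

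Results at N = 138:

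| Assumed R² | Baseline-only interval against adjusted | Type I error, baseline-only / adjusted | Power, baseline-only / adjusted |
|---|---|---|---|
| 0 | 0.4% narrower | 5.0% / 5.0% | 89.3% / 89.1% |
| 1% | 0.1% wider | 5.0% / 5.1% | 89.4% / 89.3% |
| 2% | 0.7% wider | 4.7% / 4.9% | 90.5% / 90.8% |
| 5% | 2.3% wider | 4.6% / 5.2% | 89.6% / 90.4% |
| 10% | 5.1% wider | 4.0% / 5.0% | 90.4% / 92.0% |

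In points of hardness, the half-width is 3.03 against 3.01 at R² = 2%, and 3.03 against 2.88 at 10%.

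The protocol's Part 2 design allows more: "A maximum of 200 participants will be randomised to participate in the study". At N = 200, over the same R² values, the baseline-only interval runs from 0.2% narrower to 5.2% wider. Power is 97.4 to 97.8% baseline-only and 97.4 to 98.5% adjusted.

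Adjustment breaks even at R² of about 0.8% for 138 and 0.5% for 200.

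**3. Closed-form check.** The two-sample t-test with SD 8 × √(1 − R²), at R² = 0 / 2 / 5 / 10%, gives:

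- 55 evaluable per arm: power 90.1 / 90.7 / 91.5 / 92.8%
- 80 evaluable per arm: power 97.6 / 97.8 / 98.1 / 98.5%

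**4. Could the durometers create a centre effect?** SAP 3.6 says Groningen used only the newer device, and plans a mapping for the rest: "A cross-walk methodology will be used to map the results from the old tonometer to the results of the new tonometer". Suppose the mapping leaves an offset of d points. Let p be the Groningen share, ρ the correlation between baseline and 12-month hardness, and V = 64 + d²p(1 − p). Then

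R² = 1 − 64(1 − ρ²) / [V − (64ρ + d²p(1 − p))² / V].

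With d = 2, p = 0.5 and ρ = 0.3: V = 65, the bracket is 65 − 20.2²/65 = 58.72, and R² = 1 − 58.24/58.72 = 0.8%.

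Over assumed p of 0.2 to 0.5 and ρ of 0.3 to 0.7:

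- d = 1: R² 0.04 to 0.2%
- d = 2: R² 0.2 to 0.8%
- d = 3: R² 0.4 to 1.8%

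If the mapping works, the device alone changes the interval by less than 1%.

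**5. Does the form of age matter numerically?** A second simulation used 110 evaluable participants, centre shares of 40/25/35% and a linear age effect (all but the 110 assumed; 3,000 runs for power). With age group and continuous age respectively, power was 91.5% and 91.3% at R² = 7%, and 93.0% and 93.6% at 15%. Either form works. The difficulty is having both.

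**The case against.** The strongest case is that the plan already covers this. The strata-adjusted ANCOVA is pre-specified in both documents and tabulated next to the primary result, and the documents agree on which model leads. What is left is a preference about which row is the headline. The gain is negligible at small R² and slightly negative below the break-even point, where a device offset of 1 point, and most 2-point cases, would fall. R² values of 5 to 10% rest on nothing in the documents. The change would also come late: SAP V2.0 is dated 07Jan2021 and final analysis was expected from 26Jan2021. Finally, the age mismatch may be no more than table footnotes that were never updated.

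Most of this stands, and it is why the point is optional. It does not remove the point. Analysing by the factors used to randomise costs almost nothing when they do not matter, and it corrects the interval when they do. SAP 3.6 itself allows that the cross-walk may fail, in which case centre could matter more. Whatever explains the footnotes, the current SAP still describes its adjusted model in two ways.

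**Conclusion.** The concern holds as a minor, optional point. The planned primary analysis is valid: it is unbiased, its type I error does not exceed 5% and its sample size is sufficient. Omitting the strata can only make the headline result slightly conservative. At 138 participants the effect on interval width is under 1% if the strata explain up to 2% of post-baseline variance, and about 5% if they explain 10%. At 200, power is at least 97.4% with either model. These sizes rest on an assumed R², stratum mix and block size. Values of 5 to 10% would need a failed cross-walk or a strong age or centre effect, and the documents show neither.

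The inconsistency in the form of age is certain, and should be resolved whichever model is primary.

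**What to change.** Before unblinding, make the primary analysis an ANCOVA of 12-month change on arm, baseline hardness, centre (three levels) and age group (18-49, 50 or over). Keep the baseline-only ANCOVA as supporting. If the team prefers the present primary model, give the reason.

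In either case, state one form of age:

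- **Age group:** amend SAP 3.7 (both places), 6.2 and 6.3. Protocol 11.2 and the table footnotes already agree.
- **Continuous age:** amend Protocol 11.2 (both places) and the footnotes to Table 19 and the secondary-outcome results tables. Also state how age enters the SAP 6.5 subgroup models, which use the adjusted ANCOVA but categorise age.

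The change uses 3 degrees of freedom (107 to 104 at 138 randomised, 157 to 154 at 200). If neither factor is prognostic, it widens the headline interval by about 0.4% or 0.2% respectively. It needs SAP review and sign-off under Protocol 11.7, and a protocol amendment where appropriate, in the short time before final analysis.

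It does not touch the fallback in SAP 6.2, where "the non-parametric Mann-Whitney test will be used with no adjustment for baseline". That route would remain unadjusted for the strata as well.

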### 6.2.1 Missing data

The number and proportion of individuals in the missing category will be presented, as well as reasons for missing if known. It is anticipated that there will not be a high level of missing data for the primary outcome since the blinded assessor will measure nodule hardness at each follow-up visit attended by participants. However, data could be missing if a patient withdraws or does not attend for clinical assessment.

Missing data distributions will be explored to assess whether the assumption that data are missing at random (MAR) – a core assumption under which principal analyses will be conducted – is true. If MAR can be demonstrated, multiple imputation using chained equations (MICE) will be used to impute missing data. The use of MICE in place of more simple imputation techniques allows for variability in patients disease starting point and progression to be accounted for within the imputed dataset, across all time-points. The impact of

Repurposing anti-TNF for treating Dupuytren's disease (funded by Health Innovation Challenge Fund, Wellcome Trust)

EudraCT Number: 2015-001780-40 and OCTRU Reference Number CTU0028

missing primary outcome data on modelled treatment effect will be assessed under a range of assumptions about the missing data, in which the data and missingness will be modelled jointly using a pattern-mixture model (PMM; White et al., 2018), which assesses the sensitivity of the analysis result to departures from a missing at random assumption. Sensitivity analyses, including PMM, will be run on the non-imputed ITT dataset, the non-imputed per protocol dataset and on the MICE imputed dataset to explore the missing data assumptions (see **6.2.1 – Sensitivity analysis**). Methods for handling missing data will be finalised during the blinded analysis, before the final analysis data-lock.

During the analysis, techniques other than those suggested above may be used, for instance if data are not normally distributed or in the case of new techniques being developed in the meantime. No data will be considered spurious in the analysis since all data will be checked and cleaned before analysis.

#### **6.2.2 Sensitivity analysis**

A sensitivity analysis will be carried out on a per-protocol (PP) basis to examine the robustness of the conclusions to different assumptions about departures from randomised policies. The PP population is as defined in **Section 4.2** above. Additionally, Complier Average Causal Effect (CACE) analysis will be used to assess data quality and the effect of treatment received (see **5.5 – Description of compliance with intervention** for compliance definitions). Unlike a PP analysis, CACE does not assume that those who comply with treatment are the same as those who do not. CACE analysis estimates treatment effect while accounting for whether or not participants complied with the intervention allocated to them. Further sensitivity analysis will also examine the impact of disease progression on the ability to complete follow-up assessment measures – for example, the development or presence of a new nodule in the treated finger or an adjacent finger – and the validity of multiple imputation assumptions by comparing results conducted on a dataset without any imputed values (complete case) to a dataset conducted with imputed values.

For sensitivity analyses related to Covid-19, see **Appendix 6: Response to SARS-CoV-2 Pandemic (Covid-19)**.

### **6.3 Analysis methods: Secondary outcomes**

The secondary analyses will be performed on the ITT population, comparing intervention (adalimumab) against placebo (saline, 0.9% NaCl) for all randomised participants with available data.

Mixed effects regression models will be used to analyse secondary outcomes data, with linear regression for continuous variables and logistic regression for binary variables. Mixed effects regression allows for data from all follow-up time-points to be accounted for, and for adjustment for stratification factors and baseline measurements to be made, where applicable. This procedure is robust and is able to deal with some missing values, either due to missed visits or patients leaving the study prematurely. The time (days) between baseline injection and each follow-up time-point will be included in the models as a random effect to account for patients not all having their follow-up assessments at the same time.

As per the primary outcome, initial analyses for all secondary outcomes will be unadjusted. These analyses will include only outcome measurement and treatment arm, with time since first injection included as a random effect and baseline outcome measurement as a fixed effect. Additional adjusted analyses will be carried out further accounting for centre (Oxford, Edinburgh or Groningen) and age (as a continuous variable). For all models, where appropriate, treatment by time interaction terms will be incorporated to account for changes in effects between treatment arms over follow-up.

Repurposing anti-TNF for treating Dupuytren's disease (funded by Health Innovation Challenge Fund, Wellcome Trust)  
EudraCT Number: 2015-001780-40 and OCTRU Reference Number CTU0028

For progression to surgery – a binary secondary outcome – numbers and proportions will be reported with absolute odds (odds difference) and relative odds (odds ratio), and associated 95% confidence intervals. For all continuous secondary outcomes, mean difference and associated 95% confidence intervals will be reported. For continuous measures if severe departures from normality are identified in secondary outcome measurements, the data will be log-transformed in order to gain normality and geometric means with 95% confidence intervals will be reported. If the data are not normally distributed – or near normally distributed – after log transformation, the non-parametric Mann-Whitney test will be used with no adjustment for baseline, and the median difference with 95% confidence intervals will be reported.

**Appendix 5: Outcome measure summaries, Table 10a:** Mean (with SD) nodule size, as maximal nodule feret and maximal height, recorded at each study time-point.

**Appendix 5: Outcome measure summaries, Table 10b:** Mean (with SD) nodule area recorded at each study time-point.

**Appendix 5: Outcome measure summaries, Table 11:** Mean (with SD) grip strength recorded at each study time-point.

**Appendix 5: Outcome measure summaries, Table 12a:** Mean (with SD) affected digit range of motion active measurements recorded at each study time-point.

**Appendix 5: Outcome measure summaries, Table 12b:** Mean (with SD) affected digit range of motion passive measurements recorded at each study time-point.

**Appendix 5: Outcome measure summaries, Table 13a:** Mean (with SD) Michigan Hand Outcomes Questionnaire overall score recorded at each study time-point.

**Appendix 5: Outcome measure summaries, Table 13b:** Mean (with SD) Michigan Hand Outcomes Questionnaire individual component scores recorded at each study time-point.

**Appendix 5: Outcome measure summaries, Table 14:** Mean (with SD) score for most restricted activity recorded at each study time-point.

**Appendix 5: Outcome measure summaries, Table 15:** Mean (with SD) injection experience pain score recorded at each study time-point.

**Appendix 5: Outcome measure summaries, Table 16:** Frequency and percentage of participants progressing to surgery at each study time-point

**Appendix 5: Outcome measures analysis, Table 18a:** Maximal nodule feret mixed-effects regression results for all follow-up time-points.

**Appendix 5: Outcome measures analysis, Table 18b:** Maximal nodule height mixed-effects regression results for all follow-up time-points.

**Appendix 5: Outcome measures analysis, Table 19:** Grip strength mixed-effects regression results for all follow-up time-points.

**Appendix 5: Outcome measures analysis, Table 20a:** Affected digit range of motion active measurements mixed-effects regression results for all follow-up time-points.

**Appendix 5: Outcome measures analysis, Table 20b:** Affected digit range of motion passive measurements mixed-effects regression results for all follow-up time-points.

**Appendix 5: Outcome measures analysis, Table 21:** Michigan Hand Outcomes Questionnaire mixed-effects regression results for all follow-up time-points.

Repurposing anti-TNF for treating Dupuytren's disease (funded by Health Innovation Challenge Fund, Wellcome Trust)

EudraCT Number: 2015-001780-40 and OCTRU Reference Number CTU0028

**Appendix 5: Outcome measures analysis, Table 22:** Injection experience pain score mixed-effects regression results for all follow-up time-points.

**Appendix 5: Outcome measures analysis, Table 23a:** Absolute odds of progression to surgery, from mixed-effects regression results for all follow-up time-points.

**Appendix 5: Outcome measures analysis, Table 23b:** Relative odds of progression to surgery, from mixed-effects regression results for all follow-up time-points.

**Appendix 5: Outcome measures analysis, Table 24:** Most restricted activity mixed-effects regression results for all follow-up time-points

